The term microprocessor-controlled (MPC) refers to components that are intelligently regulated in real time by one or more onboard microprocessors that modify some characteristic of their behavior according to either environmental or user inputs.¹ MPC prosthetic knees, often referred to as MPKs, are battery-powered and use algorithms based on input received from load sensors, accelerometers, gyroscopes, and joint angles to initiate the transition from stance to swing phase ²⁻⁶. MPC prosthesis have been shown to offer clinical advantages compared with mechanically controlled alternatives,⁷ and appears to be the direction of development in contemporary prosthetic research and development.⁸

The main advantage is an increased ability to allow safe ambulation ^{2,4,5,9-11}, reduced cognitive dedication to controlling the knee unit,^{2,12} reduced force required to initiate knee flexion,¹⁰ increased gait efficiency,^{2,4} and increased overall user confidence with the prosthesis ^{2,5}. The MPC knee increases comfort and improves walking speed in active users. ^{4,6,13,14} The main disadvantage has been the intolerance of dust or moisture, and its increased requirement for maintenance and repair.¹⁵

Microprocessor Controlled Knees (MPK) have become the standard of care for trans-femoral amputees of medium to high activity levels (K3-K4). While the functional principles of the different knee joints remain the same, differences in the mechanical design can be found.

The investigational device is a microprocessor-controlled prosthetic knee and employs sensory information, to automatically adapt knee damping values to match the amputee's gait requirements, accounting for variations in forward walking speed, walking terrain, user gait styles and body size. The investigational device technology generates resistances with a microprocessor-controlled, magnetorheological fluid, which enables continuous variation of knee joint resistances in both movement directions. The amount of current determines the viscosity of the fluid. Therefore, an adaptable friction moment is generated for both flexion and extension movements at the same time. In this study there are two types of comparator devices, hydraulic MPKs and previous version of the investigational device.

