Hydraulic MPKs consist of an integrated microprocessor-controlled linear hydraulic system in combination with a control algorithm. They generate knee joint resistances hydraulically with microprocessor-controlled, motorized valves. This enables continuous variations in the hydraulic resistance to be set for both movement directions. The magnetorheological fluid creates shear forces in comparison to an increase of pressure in a hydraulic system. The increased system pressure can lead to higher temperatures and risk of leakage.

The previous version of the investigational device (RK III/RK XC) features the same intended use, same clinical purpose, same user population, same placement below the socket, uses a battery powered system and is controlled through a software application that can be user configured through a separate computer interface/mobile device. The investigational device is an enhancement of the previous version, functional features and indication are equivalent to previous version and the same critical functions apply. Features that have been added include a mechanical stance locking feature that allows the user to manually lock the knee in 3 different positions in stance and the device will be waterproof. The investigational device also includes functions that were only included in the Rheo Knee XC configuration of the previous version; automatic cycling and running detection and a stair ascent mode.

Results of a pilot stage exploratory clinical investigation including 25 subjects indicate that the investigational device had similar or better performance compared to previous versions of the Rheo knee regarding satisfaction on descending activities. This investigation is designed primarily to confirm these indications and that the performance of the investigational device regarding descending activities is comparable/no worse than Rheo Knee or hydraulic MPKs.

Study Design

[figure not shown]

Figure 2 - Study design and instruments

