Repeated measures analysis has the advantage of increased power compared to group allocations and reduction in error variance associated with individual difference, as each subject acts as its own control. This is important for studying amputees as the group is a small proportion of the total population, and with specific inclusion/exclusion criteria the total eligible population becomes very small, making it difficult to find and recruit subjects to attain an acceptable level of power. This limited population pool often results in a slightly heterogeneous sample, as the amputees available are few and far between, in every sense. Furthermore, no single amputation procedure and therefore amputated stump is exactly the same, making the experience of each amputee unique. The within-subject design significantly reduces the individual differences when comparing the two conditions.

Several studies have provided evidence for the clinical performance of previous versions of the Rheo Knee, which is equivalent to the investigational device and has the same function and intended use, those are detailed in the Literature review device report [1]. The current study is due to a design iteration after modifications to the device from the previous study CIP2022022514 [9].

[figure not shown]
For full details of existing clinical data and pre-clinical data on the investigational device see Investigators Brochure [2].

7 Objectives and Hypotheses

In this trial, the primary objective is to evaluate the efficacy of the investigational device compared to the former Version Rheo Knee (XC) and in addition (mandatory) to other passive MPKs (e.g. C-leg 4, Genium, X3, Plié 3, Orion 3, Quattro, Allux) regarding performance improvements and satisfaction in descending activities for moderate to high active prosthesis users within the intended population for the investigational device.

Additionally, the overall satisfaction for activities of daily living will be evaluated after a certain time of use (4 weeks home use).

The following clinical claims/MNBA items as defined in the Clinical evaluation plan [3] are to be evaluated:

The hypothesis and endpoints are specified in Table 4 and Table 5.

For all hypothesis:

[figure not shown]
μ_1 is average of measurements at baseline (comparator);

[figure not shown]
μ_2 is the average of measurements at 4 week follow up (investigational device);

Table 5 - Endpoints, test methods and hypotheses

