8.2 Investigational Device(s) and Comparator(s)

The subjects will be asked to use the investigational device as their primary prosthesis for **4 weeks**. Individual exposure will differ between subjects. Subjects are expected to use it for their daily living activities as they would with any other prosthesis, for up to 18 hours a day depending on the amputee. The comparator device will not be used within the timeframe of the investigation. Subjects will evaluate and provide feedback on their exposure of the comparator prior to them being fitted to the investigational device.

The comparator device will be the former version Rheo Knee (XC) or any other passive microprocessor controlled prosthetic knee (excluding Kenevo as it does not have the same intended patient population as the investigational device). They have the same intended use as the investigational device. Furthermore, they are indicated for the same condition and population group. Passive MPKs are widely accepted devices, providing clinical benefits to the user.

Where possible, the subject will be using the remaining part of their current prosthetic system with the investigational device, as it was used with the comparator device. In some cases where a subject is using components from other manufacturers (e.g. feet not validated for use with the investigational device) compatible components will be provided.

No other device, medication or intervention will be used.

Up to 13 subjects are to be enrolled and therefore 13 investigational devices will be used, as the devices are intended to be used by a single patient; one for each subject.

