8.3 Subjects

All subjects will be dispositioned as follows:

- Screen Failure: Subject did not pass screening procedures, not called in for clinical visit;
- Candidate for enrollment: Passed screening procedures, accepts to come in for clinical visit;
- Enrolled: Subject signs informed consent and takes part in the first experimental session;
- Fitted: Subject leaves the clinic on the investigational device;
- Drop-out: Enrolled subject whose participation ended because they did not want to continue participation.
- Discontinued: Candidate for enrollment or Enrolled subject whose participation ended because they withdrew consent, were withdrawn by the Investigator, were lost to follow up, or died.

Table 6 Inclusion/Exclusion criteria

Inclusion:	Exclusion:
Only patients with the following characteristics are eligible for study entry:	Patients with the following characteristics are not eligible for study entry:
45Kg < body weight < 136Kg	Users with stump pain*
Cognitive ability to understand all instructions and questionnaires in the study;	Users with socket problems**
Unilateral TF/KD amputees that are regular prosthesis users for at least 3 months	Pregnant Users***
Current MPK users (passive MPKs only) regularly performing descent activities (stairs/ramps)	Users using Power Knee, Kenevo or mechanical knees as their prescribed prosthesis
Age \geq 18 years	Alignment that cannot be matched with the Navii setup, as described in Instructions for use.
Willing and able to participate in the study and follow the protocol	-Osseointegration

*Question on pain affecting their functional ability (yes/no)

**Socket fit: Socket fit comfort score over 5

*** Self reported

A subject can withdraw from participation at any time, at his/her discretion, and this will not have any consequences for the participant's treatment. In such cases a report stating reasons for discontinuation of the participant shall be prepared by the **LPI**. No further investigational procedures concerning the subject will be conducted, except for a statement explaining the reason for withdrawal, including but not limited to: interacting or interviewing the subject in order to obtain data on him/her; obtaining additional private information on the subject by either observing the subject or collecting or receiving such information from any source.

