10.1 Statistical design and procedures

The primary hypothesis will be assessed with descriptive statistics only, comparing the rates prior-evaluation (current device) and post-evaluation (investigational device). For hypotheses B, C, D, E will be assessed with mixed models effects where MPK type is used as fixed effect, subgroup analysis, and subject as random effect. F will be assessed with exploratory methods. All data will be analyzed exploratively for subgroup effects for input into further studies but not used to support claims.

Acceptance criteria for the data, as applicable, is defined in Table 4 **Endpoints, test methods and hypotheses**. Subgroup analysis will not be performed as no subgroups are defined.

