10.2 Sample size calculation

A convenience sample of up to 13 subjects are expected to complete the procedures.

For pass/fail criteria, see Table 4 **Endpoints, test methods and hypotheses**.

11 Amendments and Deviations from the Protocol (CIP)

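### The primary objective requires two comparators, but enrolment and analysis secure neither, so one comparison may rest on very few subjects

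*Combined protocol and SAP*

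**What the plan says.** The synopsis and section 7 state the same primary objective: to evaluate Navii "compared to the former Version Rheo Knee (XC) and in addition (mandatory) to other passive MPKs", with a list of examples. Section 6 treats these as two classes: "In this study there are two types of comparator devices, hydraulic MPKs and previous version of the investigational device".

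The design sections join the two with *or*. Section 8.2: "The comparator device will be the former version Rheo Knee (XC) or any other passive microprocessor controlled prosthetic knee", with Kenevo excepted. Table 6 in section 8.3 admits "Current MPK users (passive MPKs only) regularly performing descent activities (stairs/ramps", and excludes users of Power Knee, Kenevo and mechanical knees.

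The only numbers are totals over all knee types: "Up to 13 subjects are to be enrolled and therefore 13 investigational devices will be used" (section 8.2) and "A convenience sample of up to 13 subjects are expected to complete the procedures" (section 10.2). Section 8.3 requires at least 10 finishers, and sections 8.1 and 8.3 rule out replacing those who leave.

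Section 10.1 assesses the primary hypothesis descriptively. For hypotheses B to E it names a mixed model in which "MPK type is used as fixed effect". On subgroups it says three things: subgroup analysis is listed with the model, exploratory subgroup results will not support claims, and no subgroup analysis will be done because no subgroups are defined.

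In Table 5, hypothesis A compares Navii with the prescribed prosthesis, but its acceptance criterion, including the 20% limit on *worse* ratings, names Rheo Knee only.

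**The concern.** The objective is an *and*; eligibility is an *or*. Each subject serves as his or her own control against one prescribed knee. Users of other MPKs therefore contribute nothing to the comparison with Rheo Knee (XC), and Rheo users contribute nothing to the comparison marked mandatory. If one type is nearly absent, no analysis can supply the missing comparison afterwards.

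The plan could still reach a pooled conclusion in that case, because it sets no condition on the mix and no by-type result that counts towards a claim. Criterion A makes the gap visible: without Rheo users it cannot be judged as worded, and the comparison with other MPKs has no criterion of its own under A.

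**Working it through.** The plan gives no calculation to reproduce: section 10.2 states a convenience sample, with no number per comparator. The check is how often one knee type would end with very few subjects.

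**Inputs from the documents.** n = 13 enrolled (sections 8.2, 8.4 and 10.2); n = 10 finishers (section 8.3).

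**Assumptions.** The share p of candidates using the less common type is not given and is varied. Subjects arrive independently, and leaving the study is unrelated to knee type.

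**Formula.** P(X ≤ 2) = Σ C(n,k) p^k (1−p)^(n−k), for k = 0, 1, 2.

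Worked case, n = 13 and p = 0.2:
- k = 0: 0.8^13 = 0.055
- k = 1: 13 × 0.2 × 0.8^12 = 0.179
- k = 2: 78 × 0.04 × 0.8^11 = 0.268
- sum = 0.502

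| Assumed share | At most 2 of 13 | At most 2 of 10 |
|---|---|---|
| 10% | 0.87 | 0.93 |
| 20% | 0.50 | 0.68 |
| 30% | 0.20 | 0.38 |

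With a 50:50 mix either type can fall short, so the probability is doubled:
- 13 subjects: 2 × (1 + 13 + 78)/8192 = 0.02
- 10 subjects: 2 × (1 + 10 + 45)/1024 = 0.11

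**What a better mix would buy.** Taking one overall rating per subject for illustration, if none of k users rates Navii worse, the exact one-sided 95% upper bound on the true *worse* rate is 1 − 0.05^(1/k):
- k = 2: 78%
- k = 5: 45%
- k = 6: 39%
- k = 7: 35%
- k = 13: 21%

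The bound first falls below 20% at k = 14. Even a 6/7 split of 13 gives results by type that describe and do not confirm.

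**The case against.** **The operational design is pooled.** Table 5 compares Navii with the prescribed knee throughout, and section 6 itself says "comparable/no worse than Rheo Knee or hydraulic MPKs". On this view the objective is loosely worded and a pooled answer was always intended. That stands as one way to resolve the mismatch. It does not remove the word *mandatory* from the objective, which needs either data on both types or a rewrite.

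**The likelihood is unknown.** Candidates come from a selected customer base and are screened by the local investigator (section 8.4), so arrivals need not be independent and the mix may be near even. This stands: the probabilities show what could happen and do not predict it.

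**A hard quota could be costly.** Finding 5 users of a type with share p takes 5/p eligible candidates on average: 50, 25 or about 17 at 10%, 20% or 30%. Enrolment is 6 weeks at one site. This stands, and argues for a recruitment aim with a limit on the conclusion.

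**Some parts are not readable.** Figure 2, Table 4, the list of claims in section 7 and the annexes cannot be seen, so a rule by comparator there cannot be excluded. Sections 8.2 to 8.4 and 10.2, where it would belong, contain none in their readable text.

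Three stronger readings are tempting, and the documents do not support them:
- A reader might infer that with fewer than 5 users of a type, a single *worse* rating breaks the 20% limit (1/4 = 25%). That needs one rating per subject, while criterion A pools over all questions. With 3 questions each, for illustration, 4 subjects give 1/12 = 8%. Nor does any section apply the 20% within a knee type.
- A reader might infer that the fixed effect in section 10.1 could not be estimated. *MPK type* may mean Navii against the prescribed knee, since the hypotheses contrast those two and no other fixed effect is named. On that reading the mix of prescribed knees does not prevent estimation. The model also does not cover the primary hypothesis.
- A reader might infer that enrolling 13 users of one type would comply fully. It would satisfy Table 6 but not the objective in section 7.

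**Conclusion.** The point holds as a mismatch between the objective and what enrolment and analysis secure. Nothing readable prevents either required comparison from ending with two subjects or fewer. If one type is 20% of candidates or less, that happens with probability of at least 0.50 among 13 enrolled and at least 0.68 among 10 finishers; with an even mix it is 0.02 and 0.11. These figures rest on assumed shares and independent arrival.

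The consequence is a limit on what the trial may conclude about the under-represented type. It does not invalidate the within-subject comparison for the type that is well represented. The change should be made before enrolment, because the mix cannot be repaired later.

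**What to change.** Within the same total of 13:

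1. **Sections 8.3 and 8.4.** Record prescribed knee type (Rheo or other passive MPK) at the telephone screen. Aim for a balanced mix with a target minimum per type, for example 5, as a recruitment aim and not a hard quota. Five of each equals the 10 finishers already required and leaves three places free.
2. **Reporting.** Give the hypothesis A ratings and the pre/post results by comparator type, with the number of finishers in each.
3. **Section 10.1.** Reconcile the subgroup statements with this reporting, and define *MPK type*.
4. **Section 7.** State that the conclusion is limited to any comparator type reaching a pre-stated minimum of finishers. The minimum should be judged in finishers because those who leave are not replaced.

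The alternative is to restate the objective as a pooled comparison with the prescribed passive MPK and align criterion A with it.

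The cost is protocol wording, a count on the screening log and slightly more reporting. Recruitment may be slower, and the conclusion narrower, if one type is scarce. Results by type stay descriptive: 0 of 5 rating Navii worse still leaves an upper bound of 45%.

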	Hypothesis	Construct & Test Methods	Endpoints	Acceptance Criteria
A	Navii shows better or no worse results in Ramp, Stairs and Level Ground activities compared to prescribed prosthesis	Specific questions (see Annex 8.8)	Rating: Same, better, worse	Overall results for Navii are same or better than for Rheo Knee, with no more than 20% rating it worse, overall for all questions.
B	Navii shows a good level of overall satisfaction in activities of daily living	Subset of PEQ (see Annex 8.4) Specific Questions (see Annex 8.8)	PEQ Rating	Comparison Subset PEQ pre vs post. Navii not worse than prescribed.
C	Mobility is no worse with Navii compared to prescribed MPK	2 MWT	Distance walked in 2MWT (meters)	No significant reduction in distance walked on 2MWT with prescribed knee/Navii
D	Balance during ambulation is no worse with Navii compared to prescribed MPK	TUG	Time to complete TUG (seconds)	No significant increase in time needed to complete TUG with prescribed knee/Navii
E	Mobility is no worse with Navii compared to prescribed MPK	PlusM	PlusM Score	No significant reduction in PlusM Score with prescribed knee/Navii
F	Gather experiences on perceived safety and balance with Navii compared to prescribed knee.	ABC	ABC Score (0-100%)	Acceptable patient-reported perceived safety and performance

7.1 Additional Outcome measures:

8 Design of the Clinical Investigation

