8.1 General

The test will be a non-randomized single group repeated measures open label prospective design with observational and self-report measures.

Amputees are a small proportion of the general population. The population group specified in the inclusion/exclusion criteria is a further subsample of amputees. For practical reasons, i.e. to achieve statistical power, it is therefore more feasible to use within-subject comparison rather than creating study arms to compare. Furthermore, as mobile amputees generally have and use a prosthetic device for their daily activities, within-comparison is feasible comparing to the subject's previous device.

All investigational activities will be conducted at the Össur Orlando site.

As stated above the primary endpoint is Satisfaction on descending stairs, see Table 5, and the secondary endpoints are satisfaction on descending ramps, balance confidence and standing comfort in that respective order of significance. In addition, there are two exploratory endpoints on mobility and balance during ambulation. See previous chapter on objectives and hypothesis and Table 5 for rationale.

Drop-outs and withdrawals will not be replaced.

Instruments for data collection will include the following:

The Prosthesis Evaluation Questionnaire (PEQ) measures prosthetic-related quality of life. It consists of 82 items grouped into nine subscales. In addition, there are individual questions not contained in the subscales regarding satisfaction, pain, transfers, prosthetic care, self-efficacy, and importance¹⁸. This study will include a set of subscales from the PEQ, including specific questions on descending activities.

TUG The Timed Up and Go (TUG) is a tool used to test basic mobility skills by asking the subject to stand up from a chair (which should not be leaned up against a wall), walk a distance of 3 meters, turn around, walk back to the chair and sit down

2MWT is a measurement of endurance that assesses walking distance over two minutes.

ABC is a Patient-reported outcome measure that asks individuals to rate how confident they are that they will not lose their balance while performing 16 different activities.

PLUS-M (Prosthetic Limb Users Survey of Mobility) is a self-report instrument for measuring mobility of adults with lower limb amputation.

Specific questionnaire: In-house generated questionnaire on specific features in the investigational device.

Log file: User should log device use and events.

Video

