A standardized set of questions regarding the performance of the investigational device and the subject's satisfaction will be asked as a semi-structured interview, and the responses are documented.

The activities are video recorded to visually compare the performance of the two devices.

If the user feels comfortable and safe, he will be asked to use the investigational device for 4 weeks. They will be asked to fill in a log file for e.g. use in water, use of the app, use of the locking function.

The LPI will contact the user after 2 weeks to check on any issues that may arise. The user has the option to stop the trial at any time, an appointment will be made to switch to the prescribed knee.

The second visit will be at 4 weeks after visit 1. During this visit subjects will complete the same functional tests and questionnaires as at visit 1 (excluding background information) on the investigational device. They will then be fitted back to their prescribed device and feedback will be collected.

iii) Measurements and data collection

The same questionnaires, consisting of one valid instrument (subset of PEQ questions) and device and performance specific questionnaires, will be used and filled in at two separate points in time. Background information will be collected at baseline only. An activity report will be generated from the investigational device at visit 2.

Table 7 Visit schedule and procedures

	Recruitment phase: 2-4 weeks prior to baseline	Subject visit 1: baseline	Subject visit 2: 4 weeks after visit 1
Potential subjects identified, fitting inclusion/exclusion criteria, by LPI from Össur customers		X	
LPI calls potential subjects and screens by telephone (Pain Scale, SFCS)		X	
Subject signs ICF		X	
Subject answers subset of PEQ		X	
Subject performs TUG, 2MWT and activities of daily living (Ramps, stairs, uneven terrain)		X	
Subject fills in set of questionnaires (ABC, PlusM)		X	
Subject fitted with investigational device and receives training according to training protocol		X	
Subject performs activities of daily living (Ramps, stairs, uneven terrain)		X	
Subject fills in set of questionnaires (Specific questions, comparison)		X	
Subject answers subset of PEQ		X	
Subject performs TUG, 2MWT and activities of daily living (Ramps, stairs, uneven terrain)		X	
Subject fills in set of questionnaires (ABC, PlusM)		X	
LPI prints out activity report from the investigational device/ prescribed device			X

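### The primary objective speaks of performance improvements in descent, but hypothesis A and its rule test only for no worse, on pooled, unblinded subject ratings

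*Combined protocol and SAP*

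**What the plan says.** The synopsis and section 7 state the same primary objective: to evaluate the efficacy of Navii against the former Rheo Knee (XC) and, as a mandatory addition, other passive MPKs, "regarding performance improvements and satisfaction in descending activities for moderate to high active prosthesis users".

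Section 6 gives a different aim. After reporting similar or better pilot results in 25 subjects, it says the trial is meant primarily to confirm them and to confirm that "the performance of the investigational device regarding descending activities is comparable/no worse than Rheo Knee or hydraulic MPKs".

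Table 5 follows section 6. Hypothesis A reads "Navii shows better or no worse results in Ramp, Stairs and Level Ground activities compared to prescribed prosthesis". Its endpoint is "Rating: Same, better, worse" and its acceptance criterion is "Overall results for Navii are same or better than for Rheo Knee, with no more than 20% rating it worse, overall for all questions". Section 10.1 assesses the primary hypothesis with descriptive statistics only; since it deals with B to F separately, this is taken to be A.

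Section 8.1 names satisfaction on descending stairs as the primary endpoint and descending ramps as the first secondary endpoint, and refers to Table 5 for the primary. Table 5 has no row for either. Section 8.1 also says the PEQ selection includes questions on descent; in Table 5 the PEQ subset serves row B, on overall satisfaction in daily living.

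On the tests: "2MWT is a measurement of endurance that assesses walking distance over two minutes", and TUG is described as rising from a chair, walking 3 metres, turning and returning. On the filming, 8.4 says: "The activities are video recorded to visually compare the performance of the two devices".

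**The concern.** An objective that names improvement and a decision rule that tests for no worse license different conclusions. If row A is met, the report could state success under an objective of performance improvements when the rule required none. The evidence behind it would be the opinions of at most 13 subjects who know which knee they are wearing.

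The descent content is also diluted. Row A combines ramp, stairs and level ground over all questions, so good level-ground ratings can offset poor descent ratings. The endpoint that 8.1 ranks first has no criterion that could be passed or failed. Film is taken for the purpose of comparing performance, yet nothing readable says how it will be scored or where it will be reported.

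**Working it through.** **Inputs.** Up to 13 subjects (8.2, 10.2); at least 10 completers needed (8.3); limit of 20% 'worse' with no minimum share of 'better' (Table 5, row A). Section 10.2 describes a convenience sample and gives no effect size, alpha or power, so there is no planned figure to reproduce.

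**Assumption.** Each subject counts as one overall rating. The rule actually pools all questions, and the questionnaire annex is not readable, so the true denominator is unknown.

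**1. What passes.**
- All 'same': 0% worse and 0% better, so it passes at any sample size. This needs no assumption about counting.
- 13 subjects: 2/13 = 15.4% passes; 3/13 = 23.1% fails.
- 10 subjects: 2/10 = 20% passes.

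At either size the limit is 2 'worse', with no 'better' needed. The two-worse cases treat the 20% limit as the operative part of the rule. If the opening clause of the rule is read as a separate net comparison, they are arguable; the all-'same' case passes under both readings.

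**2. How often a device without benefit passes.** With true 'worse' rate w, P(pass) = sum over k = 0, 1, 2 of C(n,k) w^k (1−w)^(n−k). For 10% better, 80% same and 10% worse, w = 0.10:
- n = 13: 0.254 + 0.367 + 0.245 = 0.87.
- n = 10: 0.349 + 0.387 + 0.194 = 0.93.

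| True 'worse' rate | n = 10 | n = 13 |
|---|---|---|
| 10% | 0.93 | 0.87 |
| 20% | 0.68 | 0.50 |
| 30% | 0.38 | 0.20 |

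The true 'better' rate does not enter the formula: the probability of passing is the same whether 10% or 80% of users are better off.

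**3. What a borderline pass says.** With 2 'worse' observed, the one-sided 95% Clopper-Pearson upper limit for the true 'worse' rate is 51% at n = 10 and 41% at n = 13.

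**4. What a test of improvement would need (illustration only).** An exact one-sided sign test at 0.025, with no ties, needs 9 of 10 'better' (p = 0.0107) or 11 of 13 (p = 0.0112). Assuming 10% 'worse', the chance of success at n = 13 is 0.33 if 50% are truly 'better' and 0.65 if 70% are. The sample suits a modest claim better than an improvement claim.

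**5. Where descent appears in Table 5.**
- Row A: self-rated, with ramp and stairs pooled with level ground.
- Row B: PEQ subset with descent questions, judged on overall satisfaction.
- Rows C and D: measured tests; as described, neither involves a ramp or stair.
- Rows E and F: self-report on mobility and on balance confidence.

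No visible row has a descent-specific criterion or a descent measure other than self-report.

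**The case against.** The strongest reply is that the no-worse rule is deliberate. Section 6 states that aim, hypothesis A matches it, and any no-worse criterion passes on 'same'. That stands: the rule is not defective in itself. The fault is that the objective promises something else.

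A reader might infer that the plan has no endpoint on descent. The documents do not support this. Row A is a subject-rated comparison that covers ramps and stairs, the PEQ subset includes descent questions, and 8.1 names satisfaction on descending stairs as primary. What is absent from the readable text is a descent-specific criterion and a measure that does not depend on self-report.

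A reader might also infer that the trial cannot address its objective at all. That goes too far. The objective has a satisfaction half, which the plan addresses at least nominally. Its verb is to evaluate, and the share of 'better' ratings can be described under 10.1.

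The absence of a video endpoint must be stated with care. Table 4, the annexes, the content of 7.1, the list of clinical claims in section 7 and Figure 2 are not available in the public copy, and any of them might mention one. Filming is described only within the visit 1 sequence, so recordings on Navii at 4 weeks cannot be assumed. The readable text also does not fix the number of stairs or the slope of the ramp. A video endpoint can therefore only be a conditional addition.

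**Conclusion.** The point holds as a mismatch between objective and decision rule. Improvement is named in the synopsis and section 7, but no acceptance criterion in Table 5 requires it and no test of the primary hypothesis is planned. Row A passes with certainty when every rating is 'same'. If each subject counts once and the 20% limit decides, a device with no net benefit (10% 'worse') passes with probability 0.87 to 0.93 for 13 to 10 subjects. A pass is therefore not evidence of improvement.

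Two related inconsistencies are certain from the text: 8.1 ranks a stair-descent endpoint first that has no row in Table 5, and row A's rule compares with Rheo Knee while its hypothesis compares with the prescribed prosthesis. That the video has no scoring or endpoint is established only for the readable text.

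**What to change.** 1. Reword the primary objective in the synopsis and section 7: subject-rated performance and satisfaction in descending activities is no worse with Navii than with the prescribed passive MPK, this being either Rheo Knee (XC) or another passive MPK. Keep both comparator groups. Add a sentence that meeting row A does not support a claim of improvement. The cost is wording, and a less favourable objective.

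2. Align 8.1 with Table 5. Give the stair-descent and ramp-descent ratings their own rows, each with its own criterion, reported separately from level ground. Make the comparator in row A's rule agree with the one in its hypothesis. The cost is two table rows, provided the questionnaires already rate stair and ramp descent separately.

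3. Optionally, and only if filming at visit 2 on Navii before refit is confirmed and the same stairs and ramp are used at both visits, take from the video descent time, whether descent was step-over-step, and handrail use. Report these as supportive descriptive measures, with paired differences and confidence intervals and no pass/fail role. The cost is one CRF page and a little data entry.
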